6.11.3 Healthcare Resource Utilization (HRU)

Information on healthcare resource utilization will be collected and documented in the EDC system. This information will be collected via interview of the subject by the study staff and entered into the EDC system. General information collected may include:

- Number of visits to ANY health care professionals (HCP), other than study doctor
- Types of HCP visited (specialists versus primary care)
- Diagnostic tests performed (Yes/No)

Healthcare Resource Utilization is collected at Months 12, 15, 18, 21, 24, 27, 30, 33, and 36. Key aspects will be summarized by visit and changes over time will be explored. All the items will also be listed at subject level.

6.11.4 Sensitivity Analysis

Not applicable.

6.11.5 Exploratory Analysis

Not applicable.

6.11.6 Key Secondary Endpoints

Not applicable.

6.11.7 Other Secondary Endpoints

Not applicable.

QMD Ref: [REDACTED]	Effective: 12Aug2019	Governing QMD: [REDACTED]
Confidentiality Statement		
This document is the property of [REDACTED] and may not be duplicated, copied, altered or removed from company without prior approval from [REDACTED] or in compliance with [REDACTED].		
REF: [REDACTED]		Page 27 of 37

		Controlled Quality Management Document	
		Sponsor:	Aurinia Pharmaceuticals
		Protocol Number:	AUR-VCS-2016-02
STATISTICAL ANALYSIS PLAN. PHASE 2-3-4			

A treatment-related TEAE is defined as a TEAE that is assessed by the Investigator or Sponsor as being related to study drug. If a TEAE has a missing relationship to study drug it is assumed to be related to the study drug for analysis purposes.

A disease-related TEAE is defined as a TEAE that is assessed by the Investigator or Sponsor as being related to the disease under study. If a TEAE has a missing relationship to the disease under study it is assumed to be related to the disease under study for analysis purposes.

Missing severity assessments will be summarised as severe.

Adverse event tables will comprise tables summarizing AURORA 2 TEAEs as well as some tables summarizing all TEAEs from month 0 to month 36.

The following tables will be presented for AURORA 2 TEAEs:

- Summary table of overall incidence, the number of events, relative risk and 95% CI (voclosporin:placebo) including the following top line summaries:
 - Any AE
 - Any TEAE
 - Any Treatment-Related TEAE
 - Any Serious TEAE
 - Any Treatment-Related Serious TEAE
 - Any TEAE Leading to Voclosporin/Placebo Modification
 - Any TEAE Leading to Voclosporin/Placebo Discontinuation
 - Any TEAE Resulting to Death
 - Disease-Related TEAE
 - Disease-Related Serious TEAE
- TEAEs by System Organ Class and Preferred term
- TEAEs by System Organ Class, Preferred term and severity
- Treatment-Related TEAE by System Organ Class and Preferred Term
- Treatment-Related TEAE by System Organ Class, Preferred Term and Severity
- TEAE by System Organ Class and Preferred Term Leading to Dose Modification
- TEAE by System Organ Class and Preferred Term Leading to Voclosporin/Placebo Discontinuation
- TEAE by System Organ Class and Preferred Term Resulting in Death
- Disease-Related TEAE by System Organ Class and Preferred Term
- Serious TEAE by System Organ Class and Preferred Term

QMD Ref: [REDACTED]	Effective: 12Aug2019	Governing QMD: [REDACTED]
Confidentiality Statement		
This document is the property of [REDACTED] and may not be duplicated, copied, altered or removed from company without prior approval from [REDACTED] or in compliance with [REDACTED].		

REF: [REDACTED]

		Controlled Quality Management Document	
		Sponsor:	Aurinia Pharmaceuticals
		Protocol Number:	AUR-VCS-2016-02
STATISTICAL ANALYSIS PLAN. PHASE 2-3-4			

- Serious TEAE by System Organ Class, Preferred Term and Severity
- Treatment-Related, Serious TEAE by System Organ Class and Preferred Term
- Treatment-Related, Serious TEAE by System Organ Class, Preferred Term and Severity
- Serious TEAE by System Organ Class and Preferred Term Leading to Dose Modification
- Serious TEAE by System Organ Class and Preferred Term Leading to Voclosporin/Placebo Discontinuation
- Disease-Related, Serious TEAE by System Organ Class and Preferred Term

The following displays of AURORA 2 TEAEs will also be presented:

- Treatment-Emergent Adverse Events by Descending Frequency of Preferred Term
- Non-Serious Treatment-Emergent Adverse Events Occurring at an Incidence of >2% by Descending Frequency, System Organ Class and Preferred Term
- Treatment-Emergent Adverse Events by Descending Difference of Preferred Term between Treatment Group
- Listing of Serious TEAE
- Listing of TEAE Resulting in Death
- Listing of Post-Treatment Adverse Events Resulting in Death

The following displays will include all TEAEs from the start of AURORA 1:

- TEAE by System Organ Class and Preferred Term by Year of Onset
- Treatment-Related TEAE by System Organ Class, Preferred Term and Year of Onset
- TEAE by System Organ Class and Preferred Term Leading to Dose Modification by year of onset
- Serious TEAE by System Organ Class and Preferred Term by Year of Onset
- Treatment-Related, Serious TEAE by System Organ Class and Preferred Term and Year of onset
- Serious TEAE by System Organ Class and Preferred Term Leading to Dose Modification by year of onset

The following displays will be presented for all randomized subjects from Aurora 1?

- TEAE by System Organ Class and Preferred Term
- Serious TEAE by System Organ Class and Preferred Term

QMD Ref: [REDACTED]	Effective: 12Aug2019	Governing QMD: [REDACTED]
Confidentiality Statement		
This document is the property of [REDACTED] and may not be duplicated, copied, altered or removed from company without prior approval from [REDACTED] or in compliance with [REDACTED].		

REF: [REDACTED]

		Controlled Quality Management Document	
		Sponsor:	Aurinia Pharmaceuticals
		Protocol Number:	AUR-VCS-2016-02
STATISTICAL ANALYSIS PLAN. PHASE 2-3-4			

In counting the number of AEs reported, a continuous event (i.e., reported more than once and which did not cease), will be counted only once for a subject; a non-continuous AE reported several times by the same subject will be counted as multiple events.

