Over 90% of subjects experienced at least 1 adverse event (AE); the most common being infectious disease (56.2% low-dose, 63.6% high-dose and 50.0% placebo), GI disorders (41.6% low-dose, 52.3% high-dose and 36.4% placebo). More serious adverse events (SAEs) occurred in the voclosporin groups (25.8% low-dose, 25.0% high-dose, 15.8% placebo), and were consistent with those observed in LN patients. There were 13 (4.9%) deaths during the study. There were more deaths in the voclosporin low-dose arm (10) than in either the voclosporin high-dose (2) or placebo (1) arms, with the majority (11/13) occurring in Asia. All deaths were assessed by the Investigators as unrelated to study treatment.

In summary, no new or unexpected safety signals were observed with the use of voclosporin in LN subjects; voclosporin was generally well tolerated over a 48-week period. The overall safety profile is consistent with the expectations for the class of drug, the patient population, and concomitant therapies.

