3.1 Primary Endpoint

Adverse event (AE) profile and routine biochemical and hematological assessments. Estimand for AEs is the proportion of subjects reporting AEs in the Safety Population when comparing voclosporin and placebo at each visit. Estimands for biochemical and hematological assessments are the mean absolute values and mean changes from AURORA 1 baseline in the Safety Population when comparing voclosporin and placebo at each visit.

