4 SAMPLE SIZE

Eligible subjects will enter this study from the AURORA 1 study in order to provide the opportunity of an additional 24 months of treatment (total of 36 months of treatment); no sample size calculation is required.

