5 RANDOMIZATION

Subjects continue on the same treatment which they received in AURORA 1.

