6.1.2 Safety Population

The safety population will consist of all subjects who receive at least 1 dose of study drug in the AURORA 2 study (n=216). The subjects in this group will be analyzed based on the treatment they received. Subjects who receive voclosporin treatment for more than 14 days will be assigned to the voclosporin arm irrespective of the arm they were randomized to.

Additional safety populations will be defined as follows:

- AURORA 1 safety population (all subjects who were treated in core study, n=356) and
- subjects who did not participate in AURORA 2 (n=140).

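### For fatal and other rare rows of the AE top-line table, the only visible between-arm interval is a relative risk, which has no finite upper limit when placebo has no events; a risk difference should be added

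*SAP*

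**What the plan says.** The primary objective (Protocol 3.1, SAP 2.1) is long-term safety and tolerability compared with placebo. SAP 3.1 defines the AE part of the primary endpoint: "Estimand for AEs is the proportion of subjects reporting AEs in the Safety Population when comparing voclosporin and placebo at each visit". It names no contrast, neither a ratio nor a difference.

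The between-arm contrast appears in SAP 6.12.1 Adverse Events, in the tables for AURORA 2 treatment-emergent events. (In the available text this follows directly after 6.11.7, because the pages between are missing.) The first table is "Summary table of overall incidence, the number of events, relative risk and 95% CI (voclosporin:placebo) including the following top line summaries". It has ten rows; one is "Any TEAE Resulting to Death", and others cover serious and treatment-related serious events. The method for the interval and the handling of zero cells are not stated.

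The other places where a between-arm AE interval might be found do not supply one:

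- **Display by descending difference of preferred term (6.12.1):** no interval is mentioned.
- **Exposure-adjusted incidence rates (6.12.1.1):** rates per 100 years, with no interval and no contrast stated.
- **Rule promising 95% intervals for an odds ratio, hazard ratio or difference (6.11):** this sits under Efficacy Analyses.

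SAP 6.1.2 gives the safety population as 216 without arm sizes. SAP 4 says "no sample size calculation is required", so no precision target for AEs exists either.

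**The concern.** In a long-term safety comparison, the useful statement about a rare serious event is how large an excess on active treatment the data leave open. That is an upper limit. A ratio loses its upper limit when the denominator arm has no events, and in a study of 216 this is a likely outcome for rare rows.

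The documents themselves show that the fatal row deserves attention. In the Phase 2 study, which included the 23.7 mg twice-daily dose studied here, Protocol 1.2.4.2 reports: "There were more deaths in the voclosporin low-dose arm (10) than in either the voclosporin high-dose (2) or placebo (1) arms". All deaths there were assessed as unrelated to treatment. A continuation study that reports deaths by arm should still state what excess its data are compatible with. As written, the fatal row could show an interval that is undefined or open-ended, and nothing beside it would give the bound.

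**Working it through.** The plan states no power or precision figure for AEs, so there is none to reproduce. The base counts agree: 356 - 140 = 216 (SAP 6.1.2).

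**Inputs**
- N = 216 (SAP 6.1.2).
- Arm sizes are not given. 108 per arm is assumed; 120 voclosporin / 96 placebo is shown as a variant.
- True placebo risk of a rare event over the study is assumed at 0.5%, 1.1% and 2%. The middle value is the Phase 2 placebo death rate, 1 of about 88. The 88 is inferred: 265 randomized, less 89 low-dose (7 is 7.9%) and 88 high-dose (5 is 5.7%), from Protocol 1.2.4.2 and 1.2.5.

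**Step 1. Chance of no placebo events:** (1 - p)^n0

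| True placebo risk | n0 = 108 | n0 = 96 |
|---|---|---|
| 0.5% | 0.995^108 = 58% | 0.995^96 = 62% |
| 1.1% | 0.989^108 = 30% | 0.989^96 = 35% |
| 2% | 0.98^108 = 11% | 0.98^96 = 14% |

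**Step 2. What the relative risk interval then gives**

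The log-Wald interval is exp[ln(RR) ± 1.96 √(1/x1 - 1/n1 + 1/x0 - 1/n0)]. With x0 = 0 it is undefined. A score interval keeps a lower limit (3 v 0 events: 0.79; 4 v 0: 1.06, at 108 per arm), but its upper limit is infinite. With one placebo event an upper limit exists but is very wide: 5 v 1 gives RR 5.0 (0.59 to 42.1).

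**Step 3. What a risk difference gives**

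The Miettinen-Nurminen limits are the values δ at which

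(p̂1 - p̂0 - δ)² / {[p̃1(1 - p̃1)/n1 + p̃0(1 - p̃0)/n0] × N/(N - 1)} = 3.84,

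where p̃1 and p̃0 are the maximum likelihood estimates under p1 - p0 = δ.

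For 0 v 0 and δ > 0, p̃0 = 0 and p̃1 = δ. The upper limit is therefore 3.84 / (n1 × 215/216 + 3.84).
- At 108 per arm: 3.84 / (107.5 + 3.84) = 3.45%. By symmetry the interval is -3.5 to +3.5 points.
- At 120/96: upper 3.84 / (119.44 + 3.84) = 3.1%; lower -3.84 / (95.56 + 3.84) = -3.9%.

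Solved numerically at 108 per arm:
- 5 v 0: +1.1 to +10.4 points (about +0.2 to +9.4 at 120/96).
- 4 v 1: -1.8 to +8.3 points.

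**Step 4. What the risk difference does not cure**

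Chance that the 95% interval shows harm, by exact binomial enumeration at 108 per arm:

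| Placebo v voclosporin risk | RR, log-Wald, excludes 1 | Risk difference, Miettinen-Nurminen, excludes 0 |
|---|---|---|
| 1% v 3% | 0.6% | 16% |
| 2% v 6% | 12% | 30% |
| 15.8% v 25.8% (Phase 2 serious AEs) | 42% | 44% |

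The difference does better than log-Wald for rare events, but a tripling of a rare event would still usually go undetected. For a common row the two measures are nearly equivalent, and the RR interval is finite: 28 v 17 gives 1.65 (0.96 to 2.83).

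**The case against.** The case against has several sound parts.

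- **The SAP does not commit to log-Wald.** A reader might infer that an imbalance such as 5 v 0 deaths would get no interval at all. That is true of log-Wald only. A score interval has a lower limit, and from 4 v 0 that limit already exceeds 1. What every method loses is the upper limit.
- **The primary safety result is not left without any bound.** A reader might infer this too. Common rows give finite relative risk intervals, laboratory assessments are part of the primary endpoint, and the planned counts allow anyone to calculate a risk difference. Fatal events also appear in their own table and listings. The gap is confined to rare rows.
- **An interval that includes 1 is mainly a matter of sample size.** Step 4 shows this. It is also not true of every real excess: at the inferred Phase 2 death rates (1/88 v 10/89) the log-Wald interval would exclude 1 in 59% of trials, with 29% not estimable. Those rates come from another population over 48 weeks, whereas this study enrols subjects who completed 52 weeks of treatment, so they are weak planning values.
- **Nothing in the documents says that an interval including 1 will be read as comparable safety.** The fix guards against that reading; it does not correct a stated one.
- **Text is missing.** The opening of 6.12.1, the preceding subsections and a short stretch before 6.12.3 are not available, and an interval method or zero-event rule could stand there.

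These points narrow the concern without removing it. That readers could derive a difference from the counts is a poor substitute for fixing the measure and method before unblinding.

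**Conclusion.** The point holds for the fatal and other rare top-line rows, as a cheap improvement. In the available text the relative risk is their only between-arm interval. With 108 per arm assumed, there is roughly a 58%, 30% or 11% chance of no placebo events at true risks of 0.5%, 1.1% or 2% (62%, 35% and 14% at 120/96). In those cases no relative risk method gives a finite upper limit, whereas a score interval for the risk difference always does.

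The result rests on the assumed arm sizes and event risks, and on the missing part of 6.12.1 containing no further AE interval. It does not extend to common rows or to the primary safety endpoint as a whole, and it is not a claim that the proposed measure overcomes the limited power of 216 subjects.

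**What to change.** In SAP 6.12.1, for every row of the top-line table:

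1. Add the risk difference, voclosporin minus placebo, with a Miettinen-Nurminen score 95% interval.
2. Keep the relative risk as a supplement, shown as not estimable when an arm has no events.
3. Add a sentence that the upper limit of the risk difference is reported as the largest excess not ruled out, and that an interval including 0 (or, for the relative risk, 1) is not evidence of comparable safety.

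The cost is one column and a few lines of text, with no new data. The small downside is that the study report must state openly that excesses of several percentage points in rare events are not ruled out.

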  - 2 Visit 15 assessments marked (-) will be provided from the results of the Week 52 Visit in the AURORA study.
  - 3 Subjects who discontinue therapy will attend their regularly scheduled study visits to the end of the study. Subjects who withdraw consent and terminate the study early should be advised to attend both Visit 23 and the Safety Follow-up Visit (Visit 24).
  - 4 Subjects will have a safety follow-up visit after the last dose of study drug, and an assessment of vital status at 6 and 12 months post study.
  - 5 Unscheduled visits/assessments can be done as needed. AEs, concomitant medications and verbal compliance check should be completed.
  - 6 Abbreviated physical examination only required. Height is not required.
  - 7 At sites that are able to meet the biopsy requirements, [REDACTED]
  - 8 During the study, in the event that a subject is noted to have a QTcF value exceeding 500 msec, or >60 msec more than baseline, the ECG will be repeated; see Section 9.1.4.1, [Procedures to Manage a Treatment-Emergent Increase in QTc](#).
  - 9 Laboratory assessments will be performed according to the schedule in Section 9.1.1, [Laboratory Assessments](#); subjects will be fasting for 8 hours on the day of study entry on Month 12 (Week 52/ End of Treatment Visit of the AURORA 1 study) and at Month 24 and Month 36 End of Study visit.
  - 10 Serum pregnancy test to be evaluated at central laboratory at Month 12 using AURORA 1 Visit 15 result, Month 24, and Month 36.
  - 11 Urine pregnancy test to be performed at Month 12 (AURORA 1 Visit 15) for subjects who consent for enrollment into the AURORA 2 continuation study. In addition, urine pregnancy tests to be performed at all other visits indicated (except Month 24 and Month 36 where serum pregnancy test is performed).
  - 12 AEs will be recorded after the subject signs the ICF.
  - 13 Concomitant medications include all herbal medicines and supplements taken by the subject.
  - 14 Compliance only.
  - 15 All subjects will continue to receive oral corticosteroids starting at the same dose as at the end of the AURORA 1 study. When clinically indicated, subjects are allowed to be completely titrated off of oral corticosteroids; the sites will contact the Medical Monitor if the dose of oral corticosteroids is to be increased.
  - 16 24-hour urine collection should begin 2 days prior to the scheduled study visit in order not to coincide with the FMV sampling due on the day of the study visit.

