## **13.9 Safety Evaluations**

Specific safety endpoints are as follows:

- Biochemical (including liver function tests) and hematological laboratory tests
- AE profile and routine biochemical and hematological safety parameters
- Vital signs (BP, HR, temperature) at specific time points and change from baseline
- Standard 12-lead ECGs change from baseline
- Discontinuations from treatment
- Concomitant medications

Laboratory values, vital signs, and other safety parameters providing numeric data will be summarized by visit as absolute values and change from baseline. Laboratory values outside of defined normal ranges will be summarized.

Adverse events will be coded using the latest available version of the Medical Dictionary for Regulatory Activities, the version of which will be provided in the clinical study report.

Treatment-emergent adverse events will be summarized by treatment arm, system organ class, and preferred term. SAEs, SAEs that led to death, and SAEs/AEs that led to withdrawal will also be summarized and listed.

Only AEs which started on or after the date of first dose of study treatment in AURORA 2 will be considered TEAEs, though all AEs after informed consent will be recorded. SAEs occurring at any time after informed consent will be summarized. All concomitant medications will be summarized.

Details of these and other analyses will be provided in the SAP.

All study data analyses involving laboratory values will be based on results from the central laboratory.

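### Protocol 13.9 promises a summary of all SAEs after consent and of fatal SAEs, but the visible SAP 6.12.1 tabulates only serious and fatal TEAEs and gives post-treatment deaths a listing only

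*SAP*

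**What the plan says.** Protocol 13.9 gives TEAEs and SAEs different scopes.

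- TEAEs are bounded at the start only: "Only AEs which started on or after the date of first dose of study treatment in AURORA 2 will be considered TEAEs". No end date is given.
- SAEs are wider: "SAEs occurring at any time after informed consent will be summarized".
- Fatal events get both kinds of display: "SAEs, SAEs that led to death, and SAEs/AEs that led to withdrawal will also be summarized and listed".

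SAP 6.12.1 (numbered from the SAP's contents list) builds its tables on TEAEs.

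- General scope: "Adverse event tables will comprise tables summarizing AURORA 2 TEAEs as well as some tables summarizing all TEAEs from month 0 to month 36".
- The arm comparison is a "Summary table of overall incidence, the number of events, relative risk and 95% CI (voclosporin:placebo) including the following top line summaries". Its rows include any AE, any TEAE, any serious TEAE and any TEAE resulting in death.
- Below the top line, every serious-event table is a serious-TEAE table. The fatal-event table is "TEAE by System Organ Class and Preferred Term Resulting in Death".
- Fatal events after treatment form a separate category with one display: "Listing of Post-Treatment Adverse Events Resulting in Death".

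SAP 6.12.1.1 adds exposure-adjusted tables covering all events from both studies and names no serious or fatal subset. SAP Section 9 lists three changes from the protocol (the comparison with non-participants, the 14-day arm-assignment rule and the MMRM covariates). None concerns the scope of SAE or death reporting.

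Off-drug follow-up is planned. Footnote 3 of the Protocol's Schedule of Events says: "Subjects who discontinue therapy will attend their regularly scheduled study visits to the end of the study".

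**The concern.** Safety is the primary endpoint, and the SAP's serious-event and death tables look narrower than the protocol promised. A separate post-treatment death listing next to a TEAE death listing suggests that the SAP's TEAE window closes at or soon after last dose. If so, a subject who stops drug for toxicity and later has an SAE or dies on study would not count in the serious or fatal rows.

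That matters if stopping is unequal between arms. Protocol 1.2.5 reports that in the Phase 2 study decreased-GFR events led to permanent discontinuation in 7 (7.9%) low-dose subjects against 1 (1.1%) on placebo. The low dose there, 23.7 mg BID, is the dose studied here. Protocol 1.2.4.2 reports 10 deaths in the low-dose arm against 1 on placebo, all judged unrelated by the investigators. With few deaths expected among 216 subjects, moving a handful out of the compared table could change what it shows.

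**Working it through.** **Step 1: commitment against delivery.**

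| Item | Protocol 13.9 | Visible SAP 6.12.1 |
|---|---|---|
| SAEs | All after consent, summarized | Serious TEAEs only |
| Fatal SAEs | Summarized and listed | Fatal TEAEs tabulated; post-treatment fatal AEs listed only |
| TEAE window | Opens at first AURORA 2 dose; no end | Definition not in the reviewed text |
| Declared change | n/a | None in Section 9 |

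**Step 2: two readings of the TEAE window.**

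(a) *Open-ended, as in Protocol 13.9.* An SAE or death after stopping drug, within the reporting period, is a serious or fatal TEAE and enters the rows with relative risk and 95% CI. What remains is mainly SAEs between AURORA 2 consent and first AURORA 2 dose. That gap is short, since consent can be signed at the Month 12 visit, when study drug is dispensed. Some of these events may also appear in the serious-TEAE-by-year tables, which run from the start of AURORA 1.

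(b) *Closing at or soon after last dose.* Off-drug serious and fatal events drop out of the serious and fatal rows. They would appear only in the any-AE row and possibly the exposure-adjusted tables. The any-AE row cannot isolate them: in Phase 2 over 90% of subjects had at least one AE.

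**Step 3: illustrative size under (b).** The plan states no figure to reproduce.

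From the documents:
- Phase 2 SAEs were 25.8% (low dose) and 15.8% (placebo). Deaths were 10 and 1. The study lasted 48 weeks and randomized 265.
- Arm sizes are back-calculated: 7/0.079 = 88.6, so 89 low dose; 5/0.057 = 87.7, so 88 high dose; 265 - 89 - 88 = 88 placebo.
- The AURORA 2 safety population is 216 (216 + 140 = 356 agrees with SAP 6.1.2).

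Assumed: 216/2 = 108 per arm; stop fraction f of 0.15, 0.25 or 0.35, the same in both arms; one year of follow-up after stopping; Phase 2 rates persist off drug.

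Annual hazard h = -ln(1 - p)/(48/52):
- SAE, voclosporin: -ln(1 - 0.258)/0.923 = 0.323; placebo: -ln(1 - 0.158)/0.923 = 0.186
- Death, voclosporin: -ln(1 - 10/89)/0.923 = 0.129; placebo: -ln(1 - 1/88)/0.923 = 0.012

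One-year risk 1 - exp(-h): SAE 0.276 and 0.170; death 0.121 and 0.0123.

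Expected subjects = 108 × f × (1 - exp(-h)):

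| f | Stopped per arm | SAE, voclosporin | SAE, placebo | Deaths, voclosporin | Deaths, placebo |
|---|---|---|---|---|---|
| 0.15 | 16.2 | 4.5 | 2.8 | 2.0 | 0.2 |
| 0.25 | 27.0 | 7.5 | 4.6 | 3.3 | 0.3 |
| 0.35 | 37.8 | 10.4 | 6.4 | 4.6 | 0.5 |

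Because f is equal in both arms, the table shows how many events could fall outside the compared rows. It does not estimate a bias in the relative risk.

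**The case against.** The strongest reply is that the only TEAE definition in view, in Protocol 13.9, has no end date. On that definition off-drug SAEs and deaths are already compared by arm. The SAP also speaks of TEAEs from month 0 to month 36, which reads as a calendar window. The page on which the contents list places the start of 6.12.1 is not in the reviewed text, so the lack of a visible SAP definition is not a fault in the plan. The word post-treatment is undefined in what can be seen. It might mean only deaths at the follow-up visit, in the 30-day reporting window, or at the vital-status checks 6 and 12 months after the study.

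This stands as far as it goes. A reader might infer that SAEs and deaths after stopping drug have no arm comparison at all; the documents do not show that. Nor do they show that SAEs between consent and first AURORA 2 dose are lost on every reading, given the by-year tables from AURORA 1, the any-AE row and the exposure-adjusted tables.

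The size estimate is also open to challenge. It carries Phase 2 rates from active disease over to time off drug in subjects who completed a year of treatment. Protocol 10.3.2 can be read as ending SAE collection 30 days after last dose for subjects who discontinue early, which would shorten the assumed year. Against that, Protocol 10.3.1 runs AE reporting to Visit 24, and for deaths 10.3.2 applies whichever window is longer.

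Finally, the protocol promises a summary, not relative risks; those in the fix go beyond it and follow the SAP's own top-line format.

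None of this removes the mismatch. No visible table covers all SAEs after consent, fatal post-treatment AEs are listed but not summarized, and Section 9 is silent.

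**Conclusion.** The mismatch between Protocol 13.9 and the visible SAP 6.12.1 is established from the text; its consequence is conditional. If the SAP's TEAE window closes at or soon after last dose, as the separate post-treatment category suggests but does not prove, serious and fatal off-drug events have no dedicated comparison by arm, and unequal stopping could bias the serious and fatal relative risks. Under the stated assumptions that is roughly 4-10 against 3-6 subjects with an SAE and 2.0-4.6 against 0.2-0.5 deaths, voclosporin against placebo; these figures are illustrative only. If the window is open-ended, few events are lost. A reader might conclude that the primary safety comparison is biased in favour of voclosporin. That would need both a closed window and unequal stopping in this study, and the documents establish neither. This is a worthwhile, cheap improvement rather than a demonstrated error in the results.

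**What to change.** In SAP 6.12.1:

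1. Add a by-arm summary, by system organ class and preferred term, of all SAEs with onset after AURORA 2 consent through the end of the reporting period, regardless of treatment-emergence.
2. Add a top-line row, *Any death, on or after treatment*, with n by arm and the relative risk with 95% CI.
3. State the TEAE end date and define post-treatment. Align both with Protocol 13.9, or declare the narrower scope in Section 9.
4. Keep the existing TEAE tables and listings unchanged.

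The cost is one table, one row and a few lines of definition, from data the protocol already plans to collect, subject to resolving how Protocol 10.3.2 applies to subjects who stop drug early. The downside is that events long after stopping also reflect later treatment. The retained TEAE tables still separate these out if their window closes after last dose.
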